8.2. Safety Assessments

Planned time points for all safety assessments are provided in the SoA (Section 1.3).

8.2.1. Demographics

Demographic characteristics comprise age, year of birth, gender, race, and ethnicity (per local regulations). Source data verification will be performed on race and ethnicity unless it is prohibited by local regulations.

8.2.2. Physical Examinations

- A complete physical examination will include, at a minimum, assessments of the participant's general appearance, skin, lymph nodes, musculoskeletal/extremities, abdomen, cardiovascular, respiratory, and neurological systems.
- Height will be measured at screening only.
- Weight will also be measured at screening, baseline, and at the EoS visit. The participant is allowed to wear indoor daytime clothing with no shoes.
- Investigators should pay special attention to clinical signs related to previous serious illnesses.

8.2.3. Vital Signs

- Vital signs (to be taken before blood collection for laboratory tests) will be measured in a semi-supine position after 5 minutes rest and will include temperature, systolic and diastolic blood pressure, and pulse.
- It is recommended that the method used to measure body temperature at screening is maintained throughout the study.
- Blood pressure and pulse measurements will be assessed in a supine position with a completely automated device. Manual techniques will be used only if an automated device is not available.
- Blood pressure and pulse measurements should be preceded by at least 5 minutes of rest for the participant in a quiet setting without distractions (eg, television, cell phones).

8.2.4. Electrocardiograms

Single 12-lead ECG will be obtained after the participant has rested in a supine position for 5 minutes as outlined in the SoA (see Section 1.3) using an ECG machine that automatically calculates the heart rate and measures time between heart beats (RR), atrioventricular nodal delay (PR), duration of ventricular depolarization (QRS), total duration of ventricular depolarization (QT), and rate-corrected QT intervals using Fridericia's formula (QTcF). ECGs will be performed predose on dosing days.

8.2.5. Medical and Surgical History

Medical history will include:

- All relevant medical history (eg, significant findings, surgeries and pre-existing conditions present at screening) must be recorded in the eCRF regardless of whether it is related to gMG.
- Previous emergency room (ER) visits, hospitalizations, and intensive care unit (ICU) admissions from 1 year prior to screening, including the number of days admitted.
- Abnormalities in physical examination, vital signs and ECG at screening must be reported as medical history in eCRF. At all other visits, new abnormal or worsened pre-existing conditions will be reported as AE.

8.2.6. Clinical Safety Laboratory Assessments

- See Section 10.2 for the list of clinical laboratory tests to be performed and to the SoA (Section 1.3) for the timing and frequency. The details of sampling, handling, storage, and transportation of the samples will be described in the laboratory manual. The actual sample collection date and time must be collected in the participant's source document and included in the central laboratory data transfer.
- The investigator must review the laboratory report, document this review, and record any clinically significant changes occurring during the study as an AE. The laboratory reports must be filed with the source documents.

- All routine laboratory safety assessments must be performed by the central laboratory.
- Abnormal laboratory findings associated with the underlying disease are not considered clinically significant unless judged by the investigator to be more severe than expected for the participant's condition.
- All laboratory tests with values considered clinically significantly abnormal during participation in the study should be repeated until the values return to normal or baseline or are no longer considered clinically significant by the investigator or medical monitor.
 - If any values do not return to normal/baseline within a period of time judged reasonable by the investigator, the etiology should be identified, and the sponsor notified.
 - All protocol-required laboratory tests, as defined in Section 10.2, must be conducted in accordance with the laboratory manual and the SoA (Section 1.3).
 - If laboratory values from nonprotocol specified laboratory tests performed at the institution's local laboratory require a change in participant management or are considered clinically significant by the investigator (eg, SAE or AE or dose modification), then the outcomes must be recorded.

8.2.6.1. Hematology, Clinical Chemistry, and Urinalysis

Blood and urine samples for clinical safety laboratory assessments, including hematology, blood chemistry, and urinalysis, will be collected at the timepoints specified in the SoA (Section 1.3). The list of clinical safety laboratory parameters for hematology, clinical chemistry, and urinalysis are provided in Table 3.

- Blood samples for clinical laboratory assessments will be taken while the participant is in the fasted condition, defined as no food or drink (except for water) for 8 hours. Water is permitted up to 4 hours prior to the assessment.
- Blood samples for safety assessments will be collected according to the laboratory manual.
- The samples will be analyzed at the central laboratory.
- Clinical laboratory tests will be reviewed for potential clinically significant findings at all time points throughout the study. Findings meeting the definition of an AE (see Section 10.4) must be recorded on an AE page of the eCRF. See Section 10.4.3 for information on following up of clinically significant abnormalities.
- Laboratory tests with values considered clinically significantly abnormal during the study that meet the definition of an AE will be monitored until the values return to normal or baseline or are no longer considered clinically significant by the investigator or medical monitor.

8.2.6.2. Virus Serology

For exclusion criterion 7.a, blood will be sampled and evaluated for virus serology as described in Section 10.2.

8.2.6.3. Follicle-Stimulating Hormone Level

Female participants must have their follicle-stimulating hormone (FSH) level measured at the time points listed in the SoA (Section 1.3) as described in Section 10.2.

8.2.6.4. SARS-CoV-2 Test

Nasal and throat mucosal cell samples will be collected according to the laboratory manual at the time points specified in the SoA (Section 1.3) to be tested for SARS-CoV-2.

8.2.7. Assessment of Administration Site

The injection site of participants receiving efgartigimod PH20 SC will be continuously assessed by the participant (see Section 1.3). On dosing days, the assessment will be performed by the investigator prior to dosing and 1 hour after dosing. After participants have received efgartigimod the assessment will include asking the participants about any injection site reactions that occurred between visits. Any injection site reaction will be reported as an AE (Section 8.3).

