2.3.1. Efgartigimod Risk Assessment

Overall, efgartigimod IV has been well tolerated in healthy participants subjects as well as in patients with gMG. Efgartigimod PH20 SC was well tolerated in healthy participants. No major safety findings have arisen in ongoing and completed studies with either formulation of efgartigimod. Further information can be found in the IB⁴.

Potential Risk of Clinical Significance	Summary of Data/Rationale for Risk	Mitigation Strategy
	Study Intervention (s)	
Immune modulation leading to increased infection risk	Efgartigimod reduces IgG levels, potentially hindering immune response and increasing the infection risk. However, no opportunistic infection with efgartigimod has been observed. Efgartigimod treatment may be associated with a small increase in the frequency of infections. However, the type and severity of these infections are not different to those which patients with gMG are ordinarily susceptible. There is no increase in the type of infectious events that might be expected from high degrees of immunosuppression	Participants with clinically significant uncontrolled infections, malignancies, recent surgeries, and/or the presence of certain viral infections are excluded (see Section 5.2). Administration of efgartigimod to a participant will be interrupted if a clinically significant infection occurs. Infections are considered an adverse event of special interest (AESI) and a detailed questionnaire will be completed for any infectious events.

Potential Risk of Clinical Significance	Summary of Data/Rationale for Risk	Mitigation Strategy
	Study Intervention (s)	
	(eg, tuberculosis or opportunistic infections).	
Injection and/or infusion-related reactions (IRRs)	All therapeutic proteins have the potential to elicit antibody or other immune or nonimmune mediated responses, potentially resulting in hypersensitivity or allergic reactions such as rash, urticaria, angioedema, serum sickness, and anaphylactoid or anaphylactic reactions. None of the participants treated	Participants will be monitored at the site for 1 hour after administration and administration site reactions will be monitored continuously (see Section 1.3).
	with either efgartigimod formulation had a treatment- emergent adverse event (TEAE) that was a drug hypersensitivity or anaphylactic reaction	

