8.3.2. Method of Detecting AEs and SAEs

Care will be taken not to introduce bias when detecting AEs and/or SAEs. Open-ended and nonleading verbal questioning of the participant is the preferred method to inquire about AE occurrences.

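### Section 8.2.7 prescribes site checks, prompting and automatic AE reporting for the SC injection site only, so local reactions are ascertained unequally between the arms

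*Protocol*

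**What the plan says.** Section 8.2.7 is titled as covering the administration site, but its first sentence reads "The injection site of participants receiving efgartigimod PH20 SC will be continuously assessed by the participant". The rest follows from that sentence. "On dosing days, the assessment will be performed by the investigator prior to dosing and 1 hour after dosing". At later visits, "the assessment will include asking the participants about any injection site reactions that occurred between visits". The section closes with "Any injection site reaction will be reported as an AE (Section 8.3".

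Three other places do not limit site monitoring to one arm:

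- The Section 2.3.1 risk-table row on injection and infusion-related reactions says "Participants will be monitored at the site for 1 hour after administration and administration site reactions will be monitored continuously (see Section 1.3".
- Table 1 in Section 1.3 has a row for administration-site assessment, marked as continuous, that names no arm. Its footnote is not legible in the text available to me.
- Section 10.7.3.4 (COVID-19 appendix) lists administration site reactions among the critical parameters, again for no particular arm.

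For AEs in general, Section 8.3.2 says "Care will be taken not to introduce bias when detecting AEs and/or SAEs" and "Open-ended and nonleading verbal questioning of the participant is the preferred method to inquire about AE occurrences".

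Incidence and severity of AEs is a secondary endpoint (Section 3), summarized descriptively by arm (Section 9.4.3). The trial is open-label (Section 6.3). Section 9.2 says 76 participants would be enough for the noninferiority comparison. It raises the number to about 110 to quantify SC safety and efficacy better, with IV as the reference.

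**The concern.** Read literally, 8.2.7 has SC local reactions looked for at fixed times and asked about by name, while IV local reactions depend on general procedures. Section 2.3.3 describes most AEs with rHuPH20 as mild, transient injection site reactions. Mild, short-lived events are the kind most likely to go unrecorded unless someone looks or asks. Two arms with the same underlying reaction rate could therefore report different rates.

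The comparison at stake is one the sponsor enlarged the trial to support. A larger sample narrows the interval around the SC minus IV difference but does not remove a difference in how events are found. Blinding gives no protection either.

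**Working it through.** **Step 1. What each arm gets, on the text.**

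| Element | SC injection site | IV infusion site |
|---|---|---|
| Before dosing | Investigator site check (8.2.7) | General physical examination, scheduled at every visit (Table 1) |
| 1 hour after dosing | Investigator site check (8.2.7) | 1-hour on-site monitoring (2.3.1), with no timed site check described |
| Between visits | Continuous self-check and a question naming injection site reactions (8.2.7) | General AE questioning, preferably open (8.3.2) |
| Reporting | Every reaction is an AE (8.2.7) | General rules: new abnormalities after screening are AEs (8.2.5); abnormal safety assessments are AEs if judged clinically significant (10.4.1) |

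The physical examination covers skin and extremities when complete (8.2.2). Table 1 places activities before dosing unless otherwise indicated, so on dosing days the examination falls about a week after the previous infusion. It does not replace a look 1 hour after dosing.

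**Step 2. Consistency.** Sections 2.3.1, 1.3 (as far as it can be read) and 10.7.3.4 can be taken to promise site monitoring in both arms. Section 8.2.7 is the only full instruction that can be read, and it covers SC. A site following 8.2.7 alone would not carry out that monitoring for an infusion site.

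**Step 3. Illustration of size.** The plan states no figure to reproduce, and gives no rate for AEs or site reactions in this setting, so the rates below are assumptions.

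Let p be the any-AE incidence from general ascertainment, equal in both arms. Let q_SC and q_IV be the shares of otherwise AE-free participants in whom an active site check would add an AE.

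- As written (active check in SC only), the observed excess is (1 − p) × q_SC.
- With equal active checks, it is (1 − p) × (q_SC − q_IV).
- The part due to unequal ascertainment is the difference between these, (1 − p) × q_IV.

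If the true rates are equal (q_IV = q_SC = q), the whole observed excess is a detection effect. If q_IV is 0, none of it is. With n = 110 / 2 = 55 per arm, the 95% half-width is 1.96 × √[p(1 − p)/55 + s(1 − s)/55], where s = p + (1 − p)q is the observed SC incidence.

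| p | q | s | Excess (points) | Half-width (points) |
|---|---|---|---|---|
| 0.4 | 0.1 | 0.46 | 6 | 18.5 |
| 0.4 | 0.5 | 0.70 | 30 | 17.7 |
| 0.6 | 0.1 | 0.64 | 4 | 18.1 |
| 0.6 | 0.5 | 0.80 | 20 | 16.7 |

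First row: 0.4 + 0.6 × 0.1 = 0.46, and 1.96 × √(0.24/55 + 0.2484/55) = 0.185.

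The excess runs from 4 to 30 points against a half-width of about 17 to 19. These are ceilings for the assumed rates, because they take the true reaction rates as equal. The exercise shows only that the effect could be negligible or could exceed sampling error.

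**The case against.** The strongest reply is that IV sites are not left unobserved. Staff give the 1-hour infusion (Section 4.1), participants are monitored on site for an hour afterwards, a physical examination is scheduled at every visit, and new abnormal findings are reported as AEs. Section 8.3.2 calls open questioning the preferred method, not the only one. All of this stands. A reader might infer that IV site reactions are found only through open questioning, or that IV sites get no check at all. The documents do not support that, and the illegible Table 1 footnote may say more about who is assessed.

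A second reply is that focused checks on SC are justified, because only the SC product contains rHuPH20 and local reactions are its known effect. That is a good reason to check SC sites. It is not a reason to leave the reference arm on a different standard when the two are set side by side.

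A third is that site reactions are identifiable and can be tabulated apart. This also stands: a reader might infer that the detection effect can never be separated from other AE differences, but leaving site reactions out of the totals does that for the overall and related-AE comparisons. The comparison of local reactions themselves would still be affected.

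**Conclusion.** The point holds as unequal ascertainment and as an inconsistency between sections. As written, 8.2.7 ties the timed inspection, directed question, self-check and automatic AE rule to SC. The other places that mention the administration site name no arm.

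The likely direction is towards higher SC counts of mild local AEs and of totals that include them. The documents do not allow the amount to be estimated. The 4 to 30 points above rest on assumed rates (p of 0.4 to 0.6, q of 0.1 to 0.5, equal true reaction rates) and should not be read as an estimate of bias. Part of any SC excess would be a real effect of the route or product.

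The consequence is moderate. The AE comparison is descriptive, and the primary IgG noninferiority test does not depend on it. The change is still worth making, because the trial was enlarged partly for this safety comparison and equal ascertainment costs little.

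**What to change.** Amend 8.2.7 so that the infusion site in the IV arm gets the same check before dosing and 1 hour after, the same between-visit question worded for either route, and the same AE-reporting rule. Align Section 2.3.1, the Table 1 row with its footnote, and Section 10.7.3.4 with the amended text, so that all four say which arms are covered. Summarize AE incidence by arm both with and without administration-site reactions.

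The cost is one brief look and one question at visits where the participant is already on site, plus one extra table. If participants have already been treated under the present wording, the two-way table is still useful, and the report should state that site ascertainment differed by arm for them.

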8.2.8. Pregnancy Testing

- Refer to inclusion criteria 8.b for pregnancy testing entry criteria.
- Pregnancy testing at screening will be a highly sensitive serum test, and all subsequent pregnancy testing will be done using urine tests. Pregnancy testing should be conducted as indicated in the SoA (Section 1.3) during the study. If local regulations require more frequent or sensitive testing, then the local regulations will be followed.
- Pregnancy testing (urine or serum as required by local regulations) should be conducted at the end of relevant systemic exposure.
- Additional serum or urine pregnancy tests may be performed, as determined necessary by the investigator or required by local regulations, to establish the absence of pregnancy at any time during the subject's participation in the study.

8.2.9. Immunogenicity

8.2.9.1. ADA Against Efgartigimod

Blood samples will be collected to assess the serum levels of ADA against efgartigimod as indicated in the SoA (Section 1.3). Sampling will be done predose on IMP administration visits.

As per regulations, all samples will be analyzed in a 3-tiered approach using validated methods⁸:

1. First, all samples will be evaluated in a screening assay (tier 1) and scored as ADA positive or negative.

Clinical Study Protocol ARGX-113-2001 v2.0 Efgartigimod IV and SC

- 2. Samples that screen positive in tier 1 will be evaluated in the confirmatory ADA assay to assess the specificity of the ADA response. The samples will be scored as either confirmed positive (ie, positive immunodepletion) or confirmed negative (ie, negative immunodepletion).
- 3. Samples confirmed to be positive for ADA in tier 2 will be further analyzed in a titration assay to characterize the magnitude of the ADA response and a neutralizing antibody (NAb) assay to assess the ADA for neutralizing activity.

If no sample was taken, the reason will be recorded.

8.2.9.2. ADA Against rHuPH20

Blood samples will be collected to assess the plasma levels of ADA against rHuPH20 as indicated in the SoA (Section 1.3). Sampling will be done predose on IMP administration visits.

As per regulations, all samples will be analyzed in a 3-tiered approach using validated methods⁸:

- 1. First, all samples will be analyzed in a screening assay (tier 1), which identifies putative positive or negative samples.
- 2. Samples that screen positive in tier 1 will be evaluated in the confirmatory ADA assay to assess the specificity of the ADA response. The samples will be scored as either confirmed positive or negative.
- 3. Samples confirmed to be positive for ADA in tier 2 will be further analyzed in a titration assay to characterize the magnitude of the ADA response and a neutralizing antibody (NAb) assay to assess the ADA for neutralizing activity.

If no sample was taken, the reason will be recorded in the relevant section of the eCRF.

8.2.10. Suicidal Ideation and Behavior Risk Monitoring

- Efgartigimod is being developed for a neurologic indication, so suicidal ideation and risk behavior monitoring (SIB) is required.
- Participants being treated with efgartigimod should be monitored appropriately and observed closely for suicidal ideation and behavior or any other unusual changes in behavior, especially at the beginning and end of the course of intervention, or at the time of dose changes, either increases or decreases.
- Participants who experience signs of suicidal ideation or behavior, should undergo a risk assessment. All factors contributing to suicidal ideation and behavior (SIB) should be evaluated and consideration should be given to discontinuation of the study intervention.
- Baseline assessment of suicidal ideation and behavior and intervention emergent suicidal ideation and behavior will be monitored by asking the following question derived from the Patient Health Questionnaire (PHQ) item 9: "Over the last 2 weeks, how often have you been bothered by thoughts that you would be better off dead, or of hurting yourself in some way?"

8.3. Adverse Events (AEs), Serious Adverse Events (SAEs), and Other Safety Reporting

- The definitions of AEs and SAEs can be found in Section 10.4.
- AEs will be reported by the participant (or, when appropriate, by a caregiver, surrogate, or the participant's legally authorized representative).
- The investigator and any qualified designees are responsible for detecting, documenting, and recording events that meet the definition of an AE or SAE and remain responsible for following up AEs that are serious, considered related to the study intervention or study procedures, or that caused the participant to discontinue the study intervention (see Section 7).
- An unexpected AE is any adverse drug event, which is not listed in the reference safety information in the current IB or is not listed at the specificity or intensity that has been observed in the current study.
- Suspected adverse drug reaction means any AE for which there is a reasonable possibility that the IMP caused the AE.
- Each AE is to be evaluated for duration, severity (using the Common Terminology Criteria for Adverse Events [CTCAE] criteria version 5.0), seriousness, and causal relationship to the IMP or study procedures. The action taken with the investigational drug and the outcome of the event must also be recorded.
- The method of recording, evaluating, and assessing causality of AEs and SAEs and the procedures for completing and transmitting SAE reports are provided in Section 10.4.

8.3.1. Time Period and Frequency for Collecting AE and SAE Information

- All AEs and SAEs will be collected from the signing of the ICF until the EoS visit at the time points specified in the SoA (Section 1.3).
- All SAEs will be recorded and reported to the sponsor or designee immediately and under no circumstance should this exceed 24 hours from awareness of the site staff, as indicated in Section 10.4. The investigator will submit any updated SAE data to the sponsor within 24 hours of it being available.
- Investigators are not obligated to actively seek information on AEs or SAEs after conclusion of the study participation. However, if the investigator learns of any SAE, including a death, at any time after a participant has been discharged from the study, and he/she considers the event to be reasonably related to the study intervention or study participation, the investigator must promptly notify the sponsor.

